Title: Effects of Osteopathic Manipulative Treatment and Bio Electro-Magnetic Regulation Therapy on Low Back Pain in Adults.

NCT04704375

June 13, 2019

Principal Investigator:

[name]., M.S., M.S. (Med Ed)
Lake Erie College of Osteopathic Medicine, Bradenton Florida
[contact]
Email: [contact]

Research Title:

Effects of Osteopathic Manipulative Treatment (OMT) and Bio Electro-Magnetic Regulation (BEMER) Therapy on low back pain in adults.

Research Purpose:

The aim of this project is to investigate the individual and combined effects of Osteopathic Manipulative Treatment (OMT) and Bio Electro-Magnetic Regulation (BEMER) Therapy on low back pain in adults.

Study Summary:

It is clear that low back pain (LBP) is a major challenge in our society, which can lead to severe disability in many individuals. Although there are several different treatments and approaches to help individuals with LBP, the number affected by this condition has been steadily increasing.

OMT has been shown to be helpful in the treatment of LBP. In fact, the use of OMT has been shown to increase mobility of the lumbar myofascial tissues, visceral motion and decrease pain in patients with LBP. Bio Electro-Magnetic Regulation (BEMER) Therapy is a therapeutic modality that deploys a biorhythmically defined stimulus through a Pulsed Electromagnetic Field (PEMF), which leads to an increase in blood flow. The positive effects of BEMER on the circulation has been shown to result in significant increases in arteriovenous oxygen difference, number of open capillaries, arteriolar and venular flow volume, and flow rate of red blood cells in the microvasculature [1, 2]. Therefore, BEMER can potentially be used in the treatment of LBP by improving microcirculation in muscular tissue. In fact, BEMER with physiotherapy showed reductions in pain and fatigue acutely in patients with chronic low back pain [3]. A systemic review of randomized controlled trials that investigated whether PEMF was effective in low back pain showed there was decrease in pain intensity and improved functionality in individuals with different low back pain conditions [4].

Therefore, it is plausible that the combination of OMT and BEMER therapy may help increase circulation to myofascial structures that influence low back restriction and pain. The purpose of

this study is to investigate the individual and combined effects of OMT and BEMER therapy on low back pain.

Review of Literature:

Low back pain (LBP) has become a major challenge in our society and has a relatively high incidence and prevalence [5]. Moreover, LBP currently affects people of all ages and is a leading contributor to disease burden worldwide [6]. Individuals affected by LBP may experience this discomfort and associated disability for several months, and a proportion may remain severely disabled [7]. For nearly all people with low back pain, it is not possible to identify a specific nociceptive cause. Most people with new episodes of LBP may recover quickly; however, recurrence is common and in many cases, LBP becomes persistent and disabling [8].

Despite the overabundance of treatments and approaches devoted to LBP, this back related disability and the number of individuals affected have steadily been increasing [9, 10]. During the past three decades, changes have been made to key recommendations in national clinical practice guidelines. In fact, currently there is a bigger emphasis placed on self-management, physical and psychological therapies, and some forms of complementary medicine (such as spinal manipulation, massage, acupuncture), and less emphasis on pharmacological and surgical treatments [11].

Despite multiple clinical guidelines providing similar recommendations for managing low back pain, a substantial gap between evidence and practice exists [12]. Osteopathic manipulative treatment (OMT) is a distinctive modality used by osteopathic physicians to complement conventional management of LBP. There is considerable variability in OMT approaches when treating for LBP. Furthermore, osteopathic physicians combine conventional and complementary treatments when caring for patients with LBP. This increased variability in the approach to care for LBP patients requires more empirical data to determine the best approaches to treat LBP [13]. Franke *et al.* [14] conducted a meta-analysis that investigated the effect of OMT in LBP. The authors reported that some studies observed significant effect of OMT on pain [15-17], whereas other reported either a non-significant effect [18-20], or an effect in favor of the control treatment [19, 20]. It is clear that more research to better describe the effects of OMT on LBP is warranted.

OMT is the application of hands-on forces to help improve physiologic function and/or support homeostasis that has been negatively altered by somatic dysfunction [21], which is an impairment of function of any area of the body system [22]. These impairments can occur at the muscles, fascia, bones, joints, ligaments, vasculature, lymphatics and nerves. When somatic dysfunction is diagnosed, using an osteopaths' manual palpatory skills, it is treated with OMT. In general, OMT techniques can be classified as direct or indirect. Direct techniques such as muscle energy (ME), high velocity low amplitude (HVLA), soft tissue (ST), and myofascial release (MFR) engage the restrictive barrier and use a specifically applied force to correct the somatic dysfunction [21]. Indirect techniques such as MFR, counterstrain (CS), balanced ligamentous

tension (BLT) disengage from the restrictive barrier and the affected body part is moved into its freedom of motion [21].

The etiology of low back pain is varied from visceral causes, to a lack of adequate blood flow to the muscles and musculoskeletal imbalance. Inadequate blood supply and/or inadequate oxygen consumption can influence muscle pain [23, 24]. The role of OMT is thought to primarily address the musculoskeletal component of back pain, which may help improve muscle blood flow. Two of the primary goals of treatment with osteopathic techniques are to restore mobility and decrease pain. Using trained palpatory skills to diagnose alterations in the fascial connections within the body, it is proposed that OMT techniques can help alleviate these alterations in the body that may lead to musculoskeletal disorders such as low back pain [25]. Many studies that use OMT as the intervention to reduce low back pain, utilize a combination of direct and indirect techniques [15, 18, 26, 27]. The use of myofascial release technique has been shown to increase mobility of the lumbar myofascial tissues, visceral motion and decrease pain in patients with non-specific low back pain using ultrasound diagnostics [28].

One very promising alternative approach for the treatment of LBP is the use of Bio Electro-Magnetic Regulation (BEMER) Therapy. BEMER is a therapeutic modality that deploys a biorhythmically defined stimulus through a Pulsed Electromagnetic Field (PEMF). This stimulus has a targeted effect on the microvasculature, and the primary effect is an improvement in tissue microcirculation [3]. The positive effects of vasomotion on the microcirculation has been shown to result in significant increases in arteriovenous oxygen difference, number of open capillaries, arteriolar and venular flow volume, and flow rate of red blood cells in the microvasculature [1, 2]. Therefore, BEMER can potentially be used in the treatment of LBP by improving microcirculation in muscular tissue.

Though OMT has been shown to be effective clinically for patients in decreasing pain, little is known behind the specific mechanisms of action. It is believed all osteopathic techniques use the concepts of fascial connectivity throughout the body and therefore can help increase circulation and lymphatic flow [21, 29]. In one study, the use of OMT helped decrease autonomic and neuroendocrine markers in response to mental stress [30]. In modeled studies, OMT modalities like MFR and CS showed possible effects in modifying cytokine secretion, improving wound healing, and modifying muscle contraction [31]. These effects were shown to sometimes reverse repetitive muscle strain in the tissues. It is postulated that these strains may represent the phenomenon of somatic dysfunction. Another study showed improvement in lower extremity blood pressure, cell mass, intracellular water, basal metabolism, venous velocity, skin temperature, pain, and quality of life post MFR and physical therapy for post-menopausal women with venous insufficiency [32]. As discussed previously, BEMER therapy has been shown to increase microcirculation. BEMER with physiotherapy showed reductions in pain and fatigue acutely in patients with chronic low back pain [3]. A systemic review of randomized controlled trials that investigated whether PEMF was effective in low back pain showed there was decrease in pain intensity and improved functionality in individuals with different low back pain conditions [4]. Therefore the results from these studies suggest that the combination of

OMT and BEMER therapy can potentially help increase circulation to myofascial structures that influence low back restriction and pain.

Methodology

I. Study Design

- a. Prospective, noninvasive study to examine the individual and combined effects of OMT and Bio Electro-Magnetic Regulation (BEMER) Therapy on low back pain in adults.
- b. Study treatment location: All treatments and post treatment measurements will be performed in the osteopathic manipulative therapy laboratory at Lake Erie College of Osteopathic Medicine, Bradenton. [name] or [name], who are licensed osteopathic physicians, will be on call in the vicinity of the treatment location, however not necessarily in the room of treatment.
- c. Data Collection
 - i. After written consent is obtained, the study coordinator will assign the participant a randomized study number to de-identify the participant.
 - ii. To achieve our project's goal, we will have 4 separate groups (OMT, BEMER, OMT+BEMER, and Placebo). OMT, BEMER, and placebo treatments will be performed by osteopathic medical students who have completed additional training given by a licensed osteopathic physician, to ensure uniform technique.
 - iii. To control for anchoring bias, subjects will be randomized into one of the four groups: OMT, BEMER, OMT+BEMER, and Placebo.
 - iv. Osteopathic Manipulation Diagnosis and Treatment Protocol

Osteopathic Diagnosis and Screening

1. Observe and Palpate Thoracic and lumbar muscles for TART (tenderness, asymmetry, restriction of motion, and tenderness) changes
2. Lumbar intersegmental diagnosis: used to guide treatment with muscle energy technique
3. Counterstrain Tenderpoint screening for the following muscles: psoas major, quadratus lumborum and piriformis- used to guide treatment with counterstrain technique
4. Sacrum diagnosis: Spring test at the base of the sacrum for palpation of flexed or extended dysfunction
5. Sacroiliac dysfunction: ASIS compression test – used to lateralize somatic dysfunction at sacroiliac joints

Osteopathic Treatment/Techniques

6. Regional thoracic myofascial release technique prone
7. Lumbosacral fascia myofascial release technique prone
8. Lumbar soft tissue unilateral pressure technique prone
9. Lumbar muscle energy technique seated or lateral recumbent

10. Psoas, piriformis, quadratus lumborum counterstrain technique supine
11. Sacrum balanced ligamentous tension technique supine
12. Lumbosacral/Pelvic fascia Myofascial Release technique supine

v. Second year osteopathic medical students will perform the duties of assessing and screening for somatic dysfunction in these regions, as well as the treatment modalities (as listed above). All treatment modalities were previously learned by the students during the osteopathic principles and practices (OPP) course. In addition, the students performing the treatments will receive further training by the OPP course director and OPP clinical faculty at LECOM-Bradenton. The diagnosis/screening exam and OMT techniques will last approximately 15-20minutes.

vi. BEMER Protocol

1. Subject will lay supine on the BEMER mat, and place the B.Pad® in their lower back. BEMER mat intensity 3 will be selected in week 1, intensity 4 for week 2, and intensity 5 for week 3. B.Pad® will be set for Program 1 in week 1, Program 2 in week 2, and Program 3 in week 3. Treatments last approximately 15-20 minutes.

d. Description of Therapies used

i. OMT

1. Myofascial release (MFR) is a system of diagnosis and treatment which engages continual palpatory feedback to achieve release of myofascial tissues [33]. MFR can be performed in a direct or indirect manner. If direct MFR is being performed the area of myofascial tissue restriction is engaged for the myofascial tissues and the tissue is loaded with a constant force until tissue release occurs. If indirect MFR is being performed the area of the body with dysfunctional myofascial tissues are guided along the path of least obstruction until free movement is achieved. For this study, the student doctors will perform MFR in the thoracic, lumbar and sacral regions with the patient lying on their back and on their stomach.
2. Soft tissue (ST) is a system of diagnosis and treatment directed toward tissues other than bony or joint origins [33]. Soft tissue technique involves direct engagement of myofascial tissues and is applied with lateral stretching, linear stretching, deep pressure, traction and/or separation of muscle origin and insertion while monitoring tissue response and motion changes by palpation. Soft tissue techniques will be applied to the lumbar region in this study.
3. Muscle energy (ME) is a form of osteopathic manipulative diagnosis and treatment in which the patient's muscles are actively used on request, from a precisely controlled position, in a

specific direction, and against a distinctly executed physician counterforce [33]. The precisely directly muscle contraction from the subject, that is resisted equally by the treater, is proposed to increase tension on the Golgi tendon organ proprioceptors within a muscle [21]. Reflexively this will cause inhibition and subsequent increase in the muscle length within a hypertonic muscle [33]. This temporary increase in muscle length and relaxation are what the treater is monitoring [33]. We will use muscle energy technique in the lumbar region in either the seated or lateral recumbent position in this study.

4. Counterstrain (CS) technique is a system of diagnosis and treatment that considers the dysfunction to be a continuing, inappropriate muscle/tendon/ligament strain reflex, which is stopped by applying a position of mild strain in the direction exactly opposite to that of the reflex; this is accomplished by specific directed positioning about the point of tenderness to achieve the desired therapeutic response [33]. We will screen for counterstrain tenderpoints associated with psoas, quadratus lumborum, and piriformis muscles. These muscles have attachments to the lumbar spine, pelvis and the lower extremity and have been postulated to be a contributing factor to musculoskeletal causes of low back pain [34, 35]. Some of this techniques proposed mechanisms of action includes change in muscle spindle reflex, alpha Ia afferents and gamma efferent system with the corrective positioning [21, 33].
5. Balanced ligamentous tension (BLT) technique takes into account that all the joints in the body are balanced ligamentous articular mechanisms [21]. The ligaments provide somatosensory information that guides the muscle response for positioning the joint and the ligaments themselves guide the motion of the bony components. The goal of treatment is to balance the tension in contrasting ligaments where there is inappropriate tension present. BLT will be performed in the study in the lumbar, pelvis and sacrum. The common proposed mechanism of action for all the techniques used in the study include using the physiologic properties of connective tissue and the fascial continuum of the body to help relieve myofascial restrictions [21].

ii. Bio Electro-Magnetic Regulation (BEMER) Therapy

1. BEMER is a therapeutic modality that deploys a biorhythmically defined stimulus through Pulsed Electromagnetic Field (PEMF). This stimulus has a targeted effect on the microvasculature, and the primary effect is an improvement in tissue microcirculation [3]. The positive effects of vasomotion on the microcirculation has been shown to result in significant increases in arteriovenous

oxygen difference, number of open capillaries, arteriolar and venular flow volume, and flow rate of red blood cells in the microvasculature [1, 2]. Therefore, BEMER can potentially be used in the treatment of LBP by improving microcirculation in muscular tissue.

- iii. Placebo (Light touch, and BEMER Sham): Treaters will place their hands lightly on the subject's lumbar paraspinal muscles in the supine and prone positions in the same area as where one would place your hands for lumbar MFR technique for the same amount of time as it would take to perform MFR in this area (approximately 5 minutes). However, no lifting or action will be done. In addition, the subject will lie down on the BEMER mat (as they would do during a BEMER session), but the device will not be activated. This treatment will be used as a control.
- e. The research assistants will individually coordinate experimental times with the subjects. A licensed osteopathic physician will be in the vicinity of the treatment location at all times while treatments are being given.
- f. OMT, BEMER, and placebo will be performed by osteopathic medical students who have completed additional training given by a licensed osteopathic physician to ensure uniform technique. A licensed osteopathic physician will be in the vicinity of the treatment location at all times while treatments are being given.
- g. All data collection logs will be de-identified of personal information and only contain the randomized participant ID number linking the participant to the data collected. [name], who is one of the research coordinators, will be the data analyst.
- h. The identifying information will be maintained by the principal investigator in a locked cabinet, which he alone has access to.

II. Study Procedures and Timeline

- a. Study duration
 - i. The study duration is three weeks. The subjects will be required to have either OMT, BEMER, OMT+BEMER, or Placebo treatments during the course of the study. Each subject in the OMT groups (i.e. OMT and OMT+BEMER) will receive treatment 3 times per week for a period of 3 weeks. Subjects in the BEMER groups (i.e. BEMER and OMT+BEMER) will receive treatment 5 times per week for a period of 3 weeks. Finally, subjects in the Placebo group will receive the light touch and BEMER sham treatments at same intervals as the corresponding experimental groups. OMT, BEMER, and placebo treatments will be performed by osteopathic medical students who have completed additional training given by a licensed osteopathic physician, to ensure uniform technique.
- b. Recruitment:

- i. LECOM-Bradenton faculty, staff, osteopathic medical, dental, pharmacy, and master's students will be informed via email of the opportunity to participate in the research study and will be given contact information to confirm eligibility with a study coordinator (Appendix A).

c. Experimental Sessions

- i. Following written consent (Appendix B), subjects will be given a randomized study ID number. They will be randomized into their treatment group.
- ii. Each subject in the OMT groups (i.e. OMT and OMT+BEMER) will receive treatment 3 times per week for a period of 3 weeks. As previously mentioned, subjects in the BEMER groups (i.e. BEMER and OMT+BEMER) will receive treatment 5 times per week for a period of 3 weeks. Finally, subjects in the Placebo group will receive the light touch and BEMER sham treatments at same intervals as the corresponding experimental groups. OMT, BEMER, and placebo treatments will be performed by osteopathic medical students who have completed additional training given by a licensed osteopathic physician, to ensure uniform technique. All treatments will be performed during the span of three consecutive weeks.
- iii. Subjects will complete brief questionnaires regarding low back pain and quality of life before the beginning of study and will complete the same questionnaires following the completion of the three week treatment (Appendices C, D, E).

III. Analysis

a. Study Statistics

- i. Primary outcome variable
 1. Questionnaire ratings before and after treatments
- ii. Statistical plan including sample size justification and interim data analysis
 1. Paired T-tests (N~10 subjects) to investigate the changes in low back pain after each treatment protocol.
 2. One-Way ANOVA to investigate any statistically significant differences between the means of each of the 4 experimental groups.
- iii. Early stopping rules
 1. Any adverse effect, as determined by the attending licensed osteopathic physician. No adverse effects are anticipated.

b. Blinding

- i. All outcome analyses will be performed in a blinded fashion. Subject survey and corresponding data will be de-identified and analyzed retrospectively by investigators with no exposure to the treatment sessions. Doing so will eliminate bias associated with investigator self-interest and ensure subject anonymity.

IV. Drugs/Substances/Devices

- a. Drugs will not be used in this trial. Instead, subjects will be given osteopathic manipulative treatment, BEMER therapy, and placebo light touch.
- b. The device utilized is BEMER Pro set.

Research Participants

The target population is LECOM-Bradenton faculty, staff, osteopathic medical, dental, pharmacy, and master's students who are currently experiencing low back pain. The study will not target participants from a vulnerable or at-risk population. Our target population will be informed via email of the opportunity to participate in the research study and will be given contact information to confirm eligibility with a study coordinator.

I. Inclusion

- a. LECOM-Bradenton faculty, staff and Students currently enrolled in LECOM-Bradenton's osteopathic medical program, pharmacy program, dental program, and master's program who are currently experiencing low back pain will be approached for recruitment.

II. Exclusion

- a. Subjects will be excluded if they are unable to provide informed consent, are currently pregnant, or have a known medical history of current
 - i. Psychiatric conditions
 - ii. Skin disorders or open wounds precluding skin contact
 - iii. Fasciitis or fascial tears
 - iv. Myositis
 - v. Neurological symptoms such as numbness, tingling, weakness in lower extremities
 - vi. Neoplasia
 - vii. Cancer
 - viii. Bone fracture, osteomyelitis, or osteoporosis
 - ix. Coagulation problem
 - x. Deep vein thrombosis
 - xi. Adrenal diseases/syndromes
 - xii. Acute upper or lower respiratory infection
 - xiii. Immunosuppressive syndromes
 - xiv. Radiation or chemotherapy within the past 3 years
 - xv. Lupus
 - xvi. Osteopenia
 - xvii. Congestive heart failure
 - xviii. BMI greater than 30
 - xix. Any other autoimmune disease not stated above
 - xx. Medication changes within the last 4 weeks
 - xxi. Asthma exacerbations within the last 4 weeks
 - xxii. Immunosuppressive therapy as a consequence of organ transplantation
 - xxiii. Immunosuppressive therapy as a consequence of allogeneic cellular transplants or bone marrow stem cell transplantation

- xxiv. Other conditions often requiring immunosuppressive therapy
- xxv. Anticoagulant therapy
- xxvi. Known sensitivity to the carotid sinus reflex
- b. Subjects will be screened for eligibility based on the inclusion and exclusion criteria described above at the point of subject consent. No protected health information will be collected from subjects who are not eligible to participate in the study.
- c. If subjects develop any of the above issues during the course of the study, they will be removed from the study without penalty and will still receive compensation.

III. Definition of treatment failure or subject removal criteria

- a. Subjects who do not adhere to the full treatment regimen will be removed from the study.
- b. Subjects who experience any adverse effects from treatment, as determined by a licensed osteopathic physician, will be immediately removed from the study. However, we do not anticipate any adverse effects during the study.

Risks and Benefits

I. Risks

- a. Anticipated medical risks**
 - i. After OMT, muscle tenderness and generalized discomfort may be noted 24-48 hours after treatment in a small number of patients.
 - ii. There is little empiric data about the “hazards” to patients of student-performed procedures. Further, this study does not employ any inherently forceful techniques.
 - iii. There are no anticipated adverse effects associated with BEMER therapy.
- b. Steps taken to minimize the risks**
 - i. All Osteopathic Medical students performing osteopathic manipulation will receive additional special training by a licensed osteopathic physician, member of the LECOM-Bradenton OMM Department, and will disclose their true identity to the subjects to avoid any misconceptions that they are licensed physicians. Student-treaters will be critiqued by a physician until they are approved to perform OMT on the subjects.
 - ii. A licensed osteopathic physician will be in the vicinity of the treatment location at all times a treatment is being given.
 - iii. The operation of the BEMER Pro Set will be done by students, who will be trained by a BEMER representative. The BEMER representative will ensure students are well trained in the operation of the device. In addition, the Principal Investigator will also be available during the training and throughout the study duration to assist the students.
 - iv. There are no funds designated to compensate subjects for injury. The principal investigator will work with injured subjects to provide them with further information to the best of his ability.

c. Plan for reporting adverse events

- i. All serious or unanticipated adverse events must be reported to the LECOM IRB promptly.
- ii. All protocol amendments will be submitted to IRB for approval, with the exception of changes that must be made in order to eliminate any imminent risk of harm to subjects or to others. In this circumstance, the investigator will act to eliminate the immediate risk but must subsequently submit an appropriate protocol amendment and await approval before proceeding with the revised protocol.

II. Benefits

a. Description of probable benefits

- i. Subjects may experience a decrease in low back pain. This can translate to healthy and natural ways to improve quality of living in patients with disabling low back pain. Individually, patients could see significant increases in quality of life.
- ii. With regards to society, this study could provide patients with an efficient and inexpensive way to alleviate many of the disabilities that are associated with living with low back pain.

Consent Process and Privacy Protection

I. Consent Process

- a. Participants will be introduced to the study through classroom announcements and recruitment emails. If they decide to participate we will provide participants with a written informed consent form (Appendix B) for them to read. In addition, a researcher will thoroughly explain the study to them to ensure that the subject is willing to participate in the experiment. The participant will then sign the form after comprehension is assessed via verbal reiteration and opportunity has been provided for questions.

II. Privacy Protection/Confidentiality

- a. Any document that can be identified with the participant including informed consent, emergency information, and project data will be stored in a locked filing cabinet in the principal investigator's office. It will remain confidential unless provided with the participant's permission or required by law. Three years after completion of the study, any personal identifiers (names, addresses, birth dates, phone numbers, etc.) will be destroyed.
- b. All participants will be given a numerical subject ID to ensure anonymity. Both recorded and survey data will be labeled with study number only. This ID will also be kept in the secured, locked filing cabinet, and only the Principal Investigator will have access to these documents. The materials will be saved for three years and then shredded.
- c. Members of the research team have completed the required CITI training modules prior to working on the proposed research. Identity unlinking

procedures and use of de-identified database ensure that results of surveys and patient demographics remain confidential.

- d. We will not be making any photograph, audio, or video recordings of participants without participant consent.
- e. Our study does not involve collection of data that might produce a regulatory mandate or duty to inform authorities about potentially harmful or illegal activities.
- f. Certification of Confidentiality and application for Federal Exemption to Reporting are unnecessary.

Payment and Costs

I. Payment

- a. All subjects will receive a compensation of \$50 the form of a gift card for a local eating/shopping establishment at the time of completion of the study.
- b. Subjects who cannot complete the protocol due to adverse events will still be compensated.
- c. Subjects who are noncompliant with protocol will not receive compensation.
- d. No fees for participation
- e. No penalties for participation or non-completion

II. Costs

- a. Payment to subjects:
 - i. BEMER Pro Set: \$5,990
 - ii. 3 week compensation: \$50 per individual (estimating 40) = \$2,000
- b. Total = **\$7,990**
- c. All paid by grants TBD

Appendices

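### The BEMER sham is written as an inactive mat only, with no stated B.Pad placement, setting routine, session length or subject masking, so blinding of the only control arm is not secured

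*Combined protocol and SAP*

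**What the plan says.** **Active BEMER (Combined protocol and SAP, Methodology I.c.vi).** The set-up is "Subject will lay supine on the BEMER mat, and place the B.Pad® in their lower back". The settings then change by week: "BEMER mat intensity 3 will be selected in week 1, intensity 4 for week 2, and intensity 5 for week 3", and "B.Pad® will be set for Program 1 in week 1, Program 2 in week 2, and Program 3 in week 3". On length: "Treatments last approximately 15-20 minutes".

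**BEMER sham (I.d.iii).** The device half of the placebo is one sentence: "the subject will lie down on the BEMER mat (as they would do during a BEMER session), but the device will not be activated". The light-touch half of the same paragraph is fuller. It gives the hand position, the subject's positions and a time of about 5 minutes.

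**Frequency (II.a.i and II.c.ii).** Visit frequency is matched: "subjects in the Placebo group will receive the light touch and BEMER sham treatments at same intervals as the corresponding experimental groups".

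**Blinding (III.b).** Blinding is promised for the outcome analyses, which are done by investigators who had no exposure to the treatment sessions. The section does not mention subjects or treaters.

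**Outcome (III.a.i; Appendices C, D and E).** The primary outcome is questionnaire ratings before and after treatment. The instruments are the SF-12, a pain VAS and the Oswestry questionnaire, all completed by the subject.

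**The concern.** A sham device separates the effect of the field from the effect of believing one is treated. It does so only if subjects in the sham arm go through the same visible routine as subjects on the active device. Here the active routine has several components, and the sham text provides for only one of them, lying on the mat. A student working from this text could leave out the applicator placed at the lower back, never handle the settings, and end the session at any time. Another student could include all of these. Both would be following the protocol.

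A subject who concludes that the unit is off may rate pain and function differently for that reason alone. Blinding the analyst does not remove this, because the influence enters when the subject completes the questionnaire. Placebo is the only control arm, so the comparisons of BEMER and OMT+BEMER with Placebo have no other reference to fall back on.

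**Working it through.** The plan gives no figure on this point to reproduce. The main check is a comparison of the texts.

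**1. Active and sham text compared**

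| Element | Active BEMER (I.c.vi) | BEMER sham (I.d.iii) |
|---|---|---|
| Lying on the mat | Stated (supine) | Stated, as in a BEMER session |
| B.Pad at the lower back | Stated | Not mentioned |
| Mat intensity, weeks 1/2/3 | 3/4/5 | Not mentioned; device not activated |
| B.Pad program, weeks 1/2/3 | 1/2/3 | Not mentioned |
| Session length | About 15-20 minutes | Not mentioned |
| Control unit hidden from subject | Not mentioned | Not mentioned |

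**2. Does another section fill the gap?**

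- II.a.i and II.c.ii match visit intervals, not session content.
- III.b covers the outcome analysis only.
- Drugs/Substances/Devices IV.a names the placebo only as light touch.
- Risks and Benefits I.b.iii has a device representative train the operators. It mentions operation of the device, not a sham procedure.
- Appendix A gives a general session range of 10-30 minutes. It does not tie a length to the sham.

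None of these supplies the missing elements, and none provides for asking subjects which group they think they are in.

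**3. Extent**

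- Sham sessions per Placebo subject: 5 per week × 3 weeks = 15.
- Scheduled active BEMER time: 15 × 15 = 225 minutes to 15 × 20 = 300 minutes. Sham time cannot be computed, because no length is stated.
- Subjects affected: about 10 of 40 (N~10 per treatment protocol in III.a.ii; 40 in the cost estimate).

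**4. Hypothetical consequence**

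Assumptions, none of them from the documents:

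- the device is inert;
- belief shifts every Placebo subject's rating by δ = 0.3 to 0.5 SD relative to an active arm;
- there are n = 10 per arm;
- the test is a two-sided 5% two-sample t-test.

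The noncentrality is δ × √(n/2), with 2n − 2 = 18 degrees of freedom and a critical value of 2.101.

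- δ = 0.3: 0.3 × √5 = 0.671, rejection probability 9.7%.
- δ = 0.5: 0.5 × √5 = 1.118, rejection probability 18.5%.

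The plan names paired t-tests and a one-way ANOVA, not this pairwise test. For a four-group ANOVA with only Placebo shifted, the noncentrality is n × δ² × 3/4, with 3 and 36 degrees of freedom.

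- δ = 0.3: 10 × 0.09 × 0.75 = 0.675, rejection probability 8.8%.
- δ = 0.5: 10 × 0.25 × 0.75 = 1.875, rejection probability 16.7%.

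The nominal rate is 5% in both cases.

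**The case against.** **The sham may already include the B.Pad and the full time.** The sham sentence refers to what subjects do during a BEMER session, and I.c.vi defines that session as supine on the mat with the B.Pad in place for about 15-20 minutes. On this reading only the output is withheld. This stands in part: the B.Pad and the duration are omitted, not excluded, and a reader who infers that the sham is delivered without the B.Pad goes beyond the text. The parenthesis qualifies lying on the mat, however. It cannot reasonably supply a dummy setting routine or concealment of the unit.

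**Nothing shows that subjects can tell.** A reader might infer that the sham visibly differs and that Placebo subjects know they are untreated. The documents do not support that. They do not say whether an active session can be felt, heard or seen, where the control unit sits, or whether a display is in view. Each subject follows one arm, sessions are scheduled individually, and the recruitment email describes neither the B.Pad nor any settings. A Placebo subject thus has no documented reason to expect a change in week 2. This objection stands against any claim of actual unblinding. It does not show that masking is secured. Sensation is not the only possible cue, since a unit that is never set or switched on over 15 sessions may be informative in itself. Subjects also share one campus and include osteopathic medical students, so talk between arms is plausible, though this too is inference.

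**Detail may sit elsewhere.** The consent form was not available, so what subjects are told about a sham cannot be checked. Treaters receive training intended to make technique uniform, and sham details could be taught there. This lowers confidence about what happens in practice, but the protocol still does not define the sham.

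**The percentages have no basis in the trial.** This is correct. They illustrate a mechanism under assumed shifts and also suppose that all Placebo subjects are affected.

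**Conclusion.** The concern holds as a weakness in the written sham procedure, not as a finding that blinding fails. Compared with I.c.vi, the sham text does not provide for B.Pad placement, the weekly setting routine or the session length. No subject masking, concealment of the unit or check of group guess is stated. With self-reported outcomes and a single control arm, Placebo subjects may be able to infer that the device is off, and the likely direction of any bias favours the BEMER arms.

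The gap applies to the whole Placebo arm at every sham session. The size of any bias is unknown. The rejection rates of about 10-19% in a pairwise test, or about 9-17% in the ANOVA, are hypothetical and rest entirely on the assumed 0.3-0.5 SD shift.

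This is a cheap improvement. It is more than a missing detail, because a unit simply left off, as written, does not secure masking.

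**What to change.** - Rewrite the BEMER part of I.d.iii so that it follows I.c.vi step by step: subject supine on the mat, B.Pad placed as in the active protocol, operator going through the same weekly setting routine with no output, and the same session length as the active arm.
- In every arm that uses the mat, keep the control unit and its display out of the subject's view.
- In III.b, state who is blinded, including whether subjects are.
- After the last session, add one question asking which treatment the subject thinks they received, and report the answers by arm.

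**Cost:** protocol and training wording, a screen or a repositioned control unit, and one extra question. No further device or staff is needed. The downside is slightly longer sham sessions.
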